9.7 Other Safety Data

9.7.1 Body Weight, Body Mass Index, and Waist Circumference

For body weight, BMI, and waist circumference, descriptive statistics of measurement values and changes from baseline at each time point and the last time point (LOCF; Week 6 in the double-blind treatment period) will be calculated by treatment group and for the overall OPC-64005 group.

An analysis of the ANCOVA model with treatment group as a factor and baseline as a covariate will be performed. The least square means of each treatment group and the differences in the least square means between each OPC-64005 group and the placebo group, as well as the two-sided 95% CIs, will be calculated.

The number and proportion of subjects who meet the criteria for clinically significant body weight (Appendix 1) will be determined by treatment group and for the overall OPC-64005 group. The same analysis will also be performed by baseline BMI category (< 18.5, \geq 18.5 to < 25, \geq 25 to < 30, \geq 30). A listing of subjects who meet the criteria for clinically significant body weight (Appendix 1) will be provided.

9.7.2 Columbia-Suicide Severity Rating Scale

The number and proportion of subjects at each time point and for the entire period after the start of double-blinded IMP administration (including post-treatment observation, discontinuation, and unscheduled visits) will be determined by treatment group and for the overall OPC-64005 group for each item (suicidality, suicidal ideation, suicidal behavior, completed suicide, emergence of suicidal ideation, emergence of serious suicidal ideation, worsening of suicidal ideation, and emergence of suicidal behavior). A listing of subjects with emergence of suicidal ideation, emergence of serious suicidal ideation, worsening of suicidal ideation, and emergence of suicidal behavior will be provided. The same tabulation will be performed for each category of suicidal ideation and suicidal behavior.

- Suicidality: “Yes” to any question of suicidal ideation or suicidal behavior
- Suicidal ideation: “Yes” to any question of suicidal ideation
- Suicidal behavior: “Yes” to any question of suicidal behavior
- Emergence of suicidal ideation: Suicidal ideation is absent at baseline and present after baseline.
- Emergence of serious suicidal ideation: Suicidal ideation is absent at baseline and present with an intensity of 4 or 5 after baseline.
- Worsening of suicidal ideation: Increase in the intensity of suicidal ideation after baseline compared with baseline.
- Emergence of suicidal behavior: Suicidal behavior is absent at baseline and present after baseline.

10 Pharmacokinetic Analyses

For the plasma concentrations of OPC-64005 and OPC-144013, only listings of data will be generated without tabulation.

11 Pharmacodynamic Analyses

Not applicable.

12 Pharmacogenomic Analyses

CYP2D6 genotype (phenotype) will be tabulated as specified in [Section 7.2 Demographic and Baseline Characteristics](#).

13 Interim Analysis

No interim analyses are planned.

14 Changes in the Planned Analyses

It has been decided that CYP2D6 phenotype will be tabulated as specified in [Section 7.2](#) Demographic and Baseline Characteristics.

15 References

Not applicable.

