8.7.5 Suicidality Monitoring

8.7.5.1 Columbia-Suicide Severity Rating Scale

Suicidality monitoring will occur at the time points described in the schedule of assessments (Table 1.3-1).

This scale consists of the C-SSRS Baseline Version, which assesses a lifetime history of suicide-related events and suicidal ideation, and the C-SSRS Since Last Visit Version, which focuses on suicidality since the last visit. At screening, assessment will be performed using the C-SSRS baseline version. After screening, assessment will be performed using the since last visit version. The date and time of assessment and assessment result will be recorded in the source document and eCRF.

"Suicidal ideation" 1 and 2 will be assessed either "Yes" or "No." If 2 is "Yes," "suicidal ideation" 3 to 5 will also be assessed. If "suicidal ideation" 1 or 2 is "Yes," "intensity of ideation" will also be assessed. For "intensity of ideation," "frequency" and "duration" will be rated on 5 scales, and "controllability," "deterrents," and "reason for ideation" will be rated on 6 scales. The following "suicidal behavior" will be assessed either "Yes" or "No," and "total number" will be recorded for each "suicide attempt." If there is any suicide attempt, "actual lethality/medical damage" will be rated on 6 scales. If actual lethality/medical damage is 0, "potential lethality" will be rated on 3 scales.

Suicidal ideation:

- 1. Wish to be dead
- 2. Non-specific active suicidal thoughts
- 3. Active suicidal ideation with any methods (not plan) without intent to act
- 4. Active suicidal ideation with some intent to act, without specific plan

5. Active suicidal ideation with specific plan and intent

Suicidal behavior: Actual attempt, Non-suicidal self-injurious behavior, Interrupted attempt, Aborted attempt, Preparatory acts or behavior, Suicide (the Since Last Visit Version only)

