9.4.2.5 Other Safety Data

Body weight, body mass index (BMI) and waist circumference
 For body weight, BMI, and waist circumference, descriptive statistics of
 measurement values and changes from baseline at each time point will be calculated
 by treatment group and for the overall OPC-64005 group.
 An analysis of the ANCOVA model with treatment group as a factor and baseline as
 a covariate will be performed using the LOCF dataset. The least square means of each
 treatment group and the differences in the least square means between each OPC 64005 group and the placebo group, as well as the two-sided 95% CIs, will be

The number and proportion of subjects who meet the criteria for clinically significant body weight will be determined by treatment group and for the overall OPC-64005 group.

calculated.

C-SSRS

The number and proportion of subjects at each time point will be calculated by treatment group and for the overall OPC-64005 group for each item (suicidality, suicidal ideation, suicidal behavior, completed suicide, emergence of suicidal ideation, emergence of serious suicidal ideation, worsening of suicidal ideation, and emergence of suicidal behavior).

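### As written, the SAP's C-SSRS suicidal-behavior composite includes non-suicidal self-injury, which also affects suicidality and, in either direction, emergence of suicidal behavior

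*SAP*

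**What the plan says.** Protocol 8.7.5.1 describes how the C-SSRS is recorded. Under its suicidal-behavior heading it lists six items, each answered Yes or No: "Actual attempt, Non-suicidal self-injurious behavior, Interrupted attempt, Aborted attempt, Preparatory acts or behavior, Suicide (the Since Last Visit Version only").

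Protocol 9.4.2.5 names the rows to be tabulated by treatment group and for the pooled OPC-64005 group: "suicidality, suicidal ideation, suicidal behavior, completed suicide, emergence of suicidal ideation, emergence of serious suicidal ideation, worsening of suicidal ideation, and emergence of suicidal behavior". It does not define them.

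SAP 9.7.2 supplies the definitions. Three matter here:

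- "Suicidal behavior: “Yes” to any question of suicidal behavior"
- "Suicidality: “Yes” to any question of suicidal ideation or suicidal behavior"
- "Emergence of suicidal behavior: Suicidal behavior is absent at baseline and present after baseline"

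The same section asks for a listing of subjects with emergent suicidal behavior, and adds: "The same tabulation will be performed for each category of suicidal ideation and suicidal behavior". Baseline for safety data (SAP section 9) is the last value after the start of placebo lead-in dosing and before double-blind dosing.

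**The concern.** One of the six items is, by its own name, not suicidal. The SAP rule takes any Yes among the suicidal-behavior questions, and the only list of those questions in either document includes that item. A programmer following both texts would put a subject with self-injury alone into the suicidal-behavior row and the suicidality row. Depending on baseline, the same subject would enter the emergence row and its listing.

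The trial tests a new antidepressant, and the C-SSRS is scheduled at every visit. The exclusions at Visits 1 to 3 remove subjects with a HAM-D suicide item score of 3 or more, a Yes to C-SSRS Question 4 or 5, or high suicide risk in the investigator's judgment. True suicidal behavior should therefore be uncommon. With sparse counts, one misclassified subject is visible in the percentages. The emergence row can also err in the less comfortable direction, by leaving out a subject who has a real attempt.

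**Working it through.** The plan states no figure on this point, so there is none to reproduce. The check compares the SAP rule with the same rule after the self-injury item is left out.

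**Inputs.** Six Yes/No items from Protocol 8.7.5.1; the three definitions from SAP 9.7.2; planned group sizes of 120, 120 and 30 from Protocol 9.1.

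**Suicidal behavior.** Six items give 2^6 = 64 answer patterns.

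| Pattern | Number of patterns | Rule as written | Self-injury left out |
|---|---|---|---|
| No item Yes | 1 | No | No |
| Self-injury only | 1 | Yes | No |
| Any of the other five, with or without self-injury | 62 | Yes | Yes |

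Exactly one pattern changes.

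**Suicidality.** The same pattern changes from Yes to No, but only if no ideation item is Yes. With any ideation Yes, the subject counts under both rules.

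**Emergence of suicidal behavior.** Call the states N (nothing), S (self-injury only) and B (any of the other five). The rule as written counts N to S and N to B. With the item left out, it counts N to B and S to B. Two transitions therefore differ:

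- N to S is counted as emergent although no suicidal behavior occurred: 1 baseline pattern × 1 later pattern = 1 pair.
- S to B is not counted although suicidal behavior is new: 1 baseline pattern × 62 later patterns = 62 pairs.

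These are counts of logical patterns, not of expected subjects. S to B should be rare. After screening the C-SSRS uses the since-last-visit version, and Visit 3 falls 7 days (± 1) after Visit 2, so baseline covers only a short interval.

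**Size per affected subject**, at planned group sizes:

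- 20-mg or placebo group: 1/120 = 0.83 percentage points
- 10-mg group: 1/30 = 3.33 percentage points
- Pooled OPC-64005 group: 1/(120 + 30) = 1/150 = 0.67 percentage points

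**Can the category rows repair the composite?** Sometimes. If the composite count is 1 and self-injury is the only category with a count, the answer is plain. With overlap it is not. Take a hypothetical composite of 2 with category counts of one actual attempt, one preparatory act and one self-injury. If one subject had the attempt and the preparatory act and another had self-injury only, the correct count is 1. If one had the attempt and self-injury and another had the preparatory act, the correct count is 2. The table rows are identical in both cases.

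**The case against.** The best counter-argument is that SAP 9.7.2 does not itself list the questions. An item called non-suicidal could be read as not being a question of suicidal behavior, and the Protocol paragraph describes recording rather than scoring. SAP Appendices 4 and 5 (the lists of tables and listings) were not in the text available for this check. This reading is possible but strained: the Protocol puts the item under that heading, and nothing available gives a narrower list.

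Second, the category tabulation shows self-injury on its own row, completed suicide has a named row, and emergent cases are listed individually. Suicidal events reported as adverse events also appear in the TEAE tables. This stands as mitigation. With very few cases the rows will usually show what drove the composite. They do not correct the composite rows or the emergent listing.

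Third, a broad composite with a breakdown could be defended as cautious screening. That fits suicidal behavior and suicidality, where the rule can only over-count. It does not fit emergence, where the rule can hide a case.

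A reader might infer more: that all three rows are always inflated, that the true counts can never be recovered, or that the trial's conclusion on suicidality is unsound. The documents do not support this. Emergence is inflated only when no listed behavior was present at baseline. Sparse counts can usually be untangled. These rows carry no test or decision threshold, and nothing shows that self-injury would differ between groups.

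**Conclusion.** The point holds as a definitional error in descriptive safety outputs. Applied literally, the two documents count non-suicidal self-injury alone as suicidal behavior and, where no ideation is reported, make it the sole reason for a suicidality count. They count it as emergent suicidal behavior when baseline is clear, and they suppress a later genuine emergence when it is the only baseline finding.

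Each affected subject moves a group percentage by 0.8, 3.3 or 0.7 points (20-mg or placebo, 10-mg, pooled), assuming the safety set matches the planned group sizes. How many subjects are affected cannot be estimated from the documents and may be none. The conclusion rests on taking the Protocol's six-item list as the questions the SAP refers to. The primary efficacy analysis is not touched. The correction is worth making because the error lies in a stated rule and is nearly free to remove.

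**What to change.** In SAP 9.7.2, define suicidal behavior as Yes to any of: actual attempt, interrupted attempt, aborted attempt, preparatory acts or behavior, or suicide. State that suicidality and emergence of suicidal behavior use this list, and that for emergence it applies both at baseline and afterwards. Report non-suicidal self-injurious behavior in its own row, outside the three composites.

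The cost is a sentence or two in the SAP and one programming change. No new data, Protocol amendment or change in subject care is needed, and the self-injury cases stay visible. Suicidal-behavior and suicidality counts can only fall or stay the same. The emergent count may fall (N to S removed) or rise (S to B recovered), so the change should be made before data lock, which is when the Protocol requires the SAP to be final.
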